Progression to the Pivotal study will be based on the assessment for safety of the device and indicators of performance. Baseline and follow-up data will be used to assess any significant difference in quality of life and functional variables pre and post implant and to assess the effect of counterpulsation.

Following successful completion of this Feasibility Study, a pivotal study will be conducted to examine the safety and efficacy of the C-Pulse® system in patients in moderate to severe heart failure. The pivotal trial is expected to measure the same variables as the Feasibility Study.

The total duration of the Feasibility Study is expected to be approximately 120 months or until the study is closed.

OBJECTIVES

Primary Objectives

Following are the primary objectives for this study. The primary objective of the C-Pulse feasibility study is to assess safety, while at the same time obtain performance data for evidence of efficacy to assist planning for a pivotal study. Refer to the section on Statistical Methods and Data Analysis for a detailed discussion of the definitions and methodology.

The Clinical Investigation shall:

1. Assess the risks with regard to the performance of the device as defined by the serious adverse event rates, under normal conditions of use.
2. Assess the potential benefits of C-Pulse as defined by improvements in Peak VO₂, hemodynamic measures, quality of life and HF symptoms.

Secondary Objectives

Secondary objectives are intended to provide additional information on patient response and device performance and to allow planning for the pivotal study. The secondary objectives are as follows:

1. Further assess the potential risks with regard to the performance of the device as defined by the device failure rate, adverse event rates, adverse event attribution, re-hospitalization rates, duration of support, and length of time to hospital discharge.
2. Further assess the potential benefits of C-Pulse as defined by improvements in quality of life, fatigue impact scales, hemodynamics, average distance walked in the 6 minute hall walk test, and blood tests.
3. Assess the device usage.

Together the primary and secondary objectives will:

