This feasibility study intends to examine the effect of C-Pulse® on long-term heart failure, and to look for trends in performance indicators. This study is not powered to detect statistical significance. As such, clinical judgment is required to assess device safety and potential efficacy from data collected during this study. This clinical judgment will be provided by the DSMB.

Justification of Methodology

This study is designed as an open-label single-arm study to develop a further understanding of the C-Pulse®. It will provide safety and efficacy information for patients in whom C-Pulse® is implanted and maintain counterpulsation for six months or longer.

At six months post-procedure, the patients will provide an adverse event profile related to surgical placement of the C-Pulse® and six months employment of C-Pulse® counterpulsation. After six months of the study there will be additional information related to the adverse event profile. The patients will provide an adverse event profile for patients in whom C-Pulse® is placed and maintain counterpulsation for greater than six months.

Similarly, these patients will provide an efficacy profile. At six months post-procedure, the patients will provide information on how well a patient improves since baseline through six months of counterpulsation. After six months these patients provide additional efficacy information related to how well a patient improves since baseline through greater than six months of counterpulsation.

Primary Safety Measures

The safety of the C-Pulse® will be evaluated by reviewing a composite of the device-related adverse events through six months, as classified by the CEC. The composite device-related adverse event rate will be the percent of patients who experience at least one of the following adverse events as adjudicated by the CEC as device-related out of the total number of patients:

- Death
- Neurological Dysfunction
- Aortic Disruption
- Myocardial Infarction
- Major Infection
- Any other device-related adverse event (as adjudicated by the CEC)

The definitions for these adverse events are provided in the Adverse Event Definitions section.

Performance Requirements

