Safety will be represented in the composite device-related adverse event rate which will be reported with its 95% two-sided exact confidence interval. The composite device-related adverse event rate will be assumed to follow the Binomial Distribution. The DSMB will decide the clinical acceptability of this observed event rate in assessing trial success.

Additionally each event will be presented with its respective rate and confidence interval. Death will be separated into deaths that occur before 30-days post-procedure and those that occur between 30-days post-procedure and 6 months.

Efficacy measurements

The efficacy of C-Pulse® will be evaluated by assessing the change of the efficacy variables from baseline to 6 months post-implant. The following measurements will be taken at baseline and 6-months.

- Peak VO₂
- Quality of Life as measured by the Minnesota Living with Heart Failure (MLWHF)
- HF Symptoms as measured by NYHA
- Six Minute Hall Walk Test

Performance Requirement

Trial success will be evaluated by analyzing each patient's response to the four efficacy variables. A responder analysis will be performed for each patient assessing the response to each of the four efficacy variables. Each efficacy variable will be assessed for clinical improvement ("responder"), decline ("non-responder") or no change ("indeterminant").

Clinical improvement will be defined for each efficacy variable as:

- 1.2 ml/kg/min improvement in peak VO₂
- 7 point improvement in MLWHF score
- 1 class improvement in NYHA
- 50 meter improvement in the Six Minute Hall Walk

Clinical decline will be defined for each efficacy variable as:

- 1.2 ml/kg/min decrease in peak VO₂
- 7 point decrease in MLWHF score
- 1 class decrease in NYHA
- 50 meter decrease in the Six Minute Hall Walk

A patient that shows no improvement or decline in a particular endpoint will be labeled as "indeterminate" for that endpoint.

The overall percentage of responders, non-responders and indeterminates for each efficacy variable along with the respective 95% two-sided exact confidence interval will be presented. Additionally the point estimate for the average change and its respective standard deviation will be presented for peak VO₂, MLWHF, and the Six Minute Hall Walk. The improvement in NYHA will be presented by a cross-tabulation summary. The DSMB will decide the clinical acceptability of this responder analysis in assessing trial success.

Secondary Objectives

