The End Points for a Clinical Trial are chosen according to the severity of disease in the population selected. The target population for this trial has been defined widely to include patients with the best natural history compatible with the degree of certainty that the device will provide an improvement. This will help maximize the generalization of the results. The primary endpoint should be clinically relevant and sensitive to the hypothesized effect of the treatment. End-points should be obtainable in all patients and be inexpensive to measure. Endpoints may include clinical outcomes such as death or morbid events such as repeat hospitalizations, or measures of quality of life such as NYHA Class or QOL scores. Surrogate measures of heart failure for heart assist devices have not been established but may strengthen a trial by showing correlation with clinically relevant findings. Composite endpoints may include clinical outcomes and surrogates, but should avoid combining safety and efficacy outcomes; composite structure has the advantage of reducing sample size, though selection of composites requires that the treatment has similar affect for all endpoints selected.

The C-Pulse® is targeted at Class III–IV patients, where mortality is difficult to predict, but the quality of life of patients is poor enough to consider the need for an implantable heart assist device. The primary endpoint in this Feasibility study is safety, and will be assessed by showing the device is not associated with an unacceptable mortality or morbidity profile in the selected patient population, as judged by the DSMB. Performance variables will allow statistical planning of the Pivotal study and selection of appropriate endpoints and study design.

Studies regarding NYHA Class III and IV patients also are useful to identify boundaries of expected changes in endpoints.

Summary

The objective of the feasibility clinical investigation shall be related to establishing or verifying the safety, and identify trends of efficacy and performance of the device, when used for its intended purpose and according to the documented instructions. The study may be expanded to a pivotal randomized double-blinded trial after taking into account the serious adverse event profile and anticipated levels of performance and efficacy as compared to other circulatory support devices.

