PRIMARY OBJECTIVES	
The primary objective of the C-Pulse feasibility study is to assess safety, while at the same time obtain performance data for evidence of efficacy to assist planning for a pivotal study. Refer to the section on Statistical Methods and Data Analysis for a detailed discussion of the definitions and methodology.
 
The Clinical Investigation shall:
 
 1. Assess the risks with regard to the performance of the device as defined by the serious adverse event rates, under normal conditions of use. 2. Assess the potential benefits of C-Pulse as defined by improvements in Peak VO₂, hemodynamic measures, quality of life and HF symptoms.
SECONDARY OBJECTIVES	
Secondary objectives are intended to provide additional information on patient response and device performance and to allow planning for the pivotal study. The secondary objectives are as follows:
 
 1. Further assess the potential risks with regard to the performance of the device as defined by the device failure rate, adverse event rates, adverse event attribution, re-hospitalization rates, duration of support, and length of time to hospital discharge. 2. Further assess the potential benefits of C-Pulse as defined by improvements in quality of life, fatigue impact scales, hemodynamics, average distance walked in the 6 minute hall walk test, and blood tests. 3. Assess the device usage

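### Primary objective 1 is defined by serious adverse events, but the only overall primary safety rate counts device-related events, serious or not

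*Combined protocol and SAP*

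**What the plan says.** The Primary Objectives section gives the first objective as "Assess the risks with regard to the performance of the device as defined by the serious adverse event rates, under normal conditions of use". Appendix R repeats it, and both places refer to the statistical section for definitions and methodology. The Summary that closes the justification for the investigation says the study may be expanded to a pivotal trial "after taking into account the serious adverse event profile and anticipated levels of performance and efficacy as compared to other circulatory support devices".

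In the statistical section, Primary Safety Measures says safety is "evaluated by reviewing a composite of the device-related adverse events through six months, as classified by the CEC". The rate is the share of patients with one or more events that the Clinical Events Committee (CEC) attributes to the device. The list is death, neurological dysfunction, aortic disruption, myocardial infarction and major infection, followed by a catch-all for every other device-related event. No component carries a seriousness condition. Performance Requirements reports the composite with an exact two-sided 95% interval and adds: "The DSMB will decide the clinical acceptability of this observed event rate in assessing trial success". Each event also gets its own rate and interval, and "Death will be separated into deaths that occur before 30-days post-procedure" and later deaths up to six months.

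The statistical section's Secondary Objectives give each defined event type a rate with an exact interval. They also tabulate events by CEC-judged seriousness, device-relatedness and procedure-relatedness.

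**The concern.** The objective and its analysis describe different quantities. The objective is defined by seriousness. The composite is defined by device attribution and ignores seriousness. Yet the composite is the figure that stands for safety, and its acceptability is what the data and safety monitoring board (DSMB) is asked to judge.

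What is at stake is the reading of the headline result. A team that follows the plan exactly will report a rate and interval that do not estimate what objective 1 names. It will have no defined rate behind the serious-event criterion for moving to a pivotal trial. In a single-arm surgical study of 20 to 40 patients, a handful of operative events attributed to the procedure, or of minor driveline infections, could separate the two quantities noticeably.

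**Working it through.** The plan states no event rate, threshold or precision target for safety, so there is no figure to reproduce. The check sets the definitions side by side and then works out how the two rates can differ.

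**1. Definitions**
- *Serious* (Adverse Event Classification): death, threat to life, surgical intervention, permanent disability, or new or unduly prolonged hospitalization. Relatedness plays no part.
- *Device-related* (same section): caused or affected by the presence or operation of the device. Seriousness plays no part.
- *Procedure-related* (same section): caused by the implantation and not directly attributable to a particular device or tool.

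**2. Events that separate the two rates**
- Bleeding that needs re-operation is Major Bleeding and is serious. If the CEC judges it procedure-related only, it adds nothing to the composite.
- A culture-positive driveline-site infection with clinical signs, treated with antimicrobials, falls under Major Infection. Treated without admission or surgery, it need not meet any seriousness criterion. If judged device-related, it counts in full.
- Table 5 (Unavoidable Events) removes some minor early events from reporting, but not an infection of this kind.

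**3. Difference between the rates**

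Let A be the patients with at least one reportable device-related event, S the patients with at least one serious event, and n the number implanted. Then

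composite − serious event rate = (number in A but not S − number in S but not A) / n.

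Either term can be the larger, so the sign is not fixed. A patient in both sets contributes nothing. One patient in only one set moves the difference by 1/40 = 2.5 points (expansion size, Study Size and Duration) or 1/20 = 5 points (Sample Size Determination).

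**4. Do other planned outputs give the serious event rate?**
- *Per-event rates.* They mix serious with non-serious events and cannot be added, because one patient can have several. If m event types each occur in a patients, the share with at least one lies between a/n and min(n, m·a)/n. With assumed m = 3 and a = 4 at n = 40, that is 4/40 = 10.0% (exact 95% interval 2.8–23.7) to 12/40 = 30.0% (16.6–46.5). With m = 3 and a = 2 at n = 20, it is 2/20 = 10.0% (1.2–31.7) to 6/20 = 30.0% (11.9–54.3). These counts are invented. They bear only on the per-event lines, not on the seriousness table.
- *Seriousness tabulation.* This is the closest output. The section says categorical variables get frequency and percent. It does not say whether this table counts patients or events, fixes no six-month window for it, and attaches exact intervals to event types rather than to seriousness.
- *Adverse event rate by visit.* The same section lists a rate at 3, 6, 12 and 18 months and annually for years 2–5, as an endpoint consistent with the primary objectives. It mentions no seriousness criterion.

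**5. Deaths**

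The split by period follows a list confined to device-related events, and the text does not say whether it covers all deaths. Primary Safety Measures says "The definitions for these adverse events are provided in the Adverse Event Definitions section", but death has no entry there. Secondary Objectives mention mortality only as survival duration.

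**6. Would the missing rate be usable?**

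The plan's own exact method gives limits Beta⁻¹(0.025; x, n−x+1) and Beta⁻¹(0.975; x+1, n−x). With an assumed 40%, 8/20 gives 19.1–63.9% and 16/40 gives 24.9–56.7%. That is wide, but it is the same precision the composite has at an equal count.

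**The case against.** The strongest reply is that objective 1 concerns risk tied to the performance of the device and speaks of rates in the plural, so a device-related composite with per-event rates is a fair reading. The study has no hypothesis test and no numeric limit. The DSMB uses clinical judgment and is asked about a mortality and morbidity profile, not one number. It would also see procedure-relatedness, seriousness and all-cause re-hospitalization tabulated.

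Much of this stands. A reader might infer that the planned tables cannot yield the serious event rate. The documents do not support that: if the seriousness table counts patients, the proportion is there and its interval follows from x and n. What is missing is the counting unit, the window and the interval. Nor is the composite the only primary rate, since Performance Requirements adds per-event rates; it is the only overall one. It would also be wrong to infer that the board would not see procedure-related serious events, or that all-cause mortality goes unrecorded. Every death must be documented and is reviewed by the CEC.

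The reply does not remove the mismatch. Even on the narrow reading, the seriousness criterion named in the objective is absent from the rate that represents safety. Seriousness appears only in an analysis attached to the secondary objectives. Rewording objective 1 to match the composite would remove the contradiction, but would leave the pivotal-trial criterion in the Summary without a defined rate.

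**Conclusion.** The point holds as a mismatch between objective and analysis and should be fixed. The overall primary safety rate omits serious events judged not device-related and includes non-serious device-related ones, so it does not estimate what objective 1 names. Whether the death split is all-cause is genuinely unclear.

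The size is unknown, because the documents give no event counts. The step is 2.5 points per patient at 40 implanted or 5 points at 20, in either direction. A reader might infer that the composite understates risk; the documents fix no direction. Nor should the 10% to 30% range in the working be read as the size of the error. It rests on assumed counts and shows only that per-event rates cannot be summed.

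Two further demands would go beyond the defect. A co-primary label is unnecessary because nothing is tested. A separate report on patients anesthetized but not implanted is not needed for this point, since they are followed and Subjects for Analysis already plans a secondary analysis of all followed-up subjects.

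**What to change.** Keep the device-related composite. Beside it, in Primary Safety Measures and Performance Requirements, report for implanted patients, each with an exact 95% interval:

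1. the percent with at least one CEC-adjudicated serious adverse event through six months, regardless of relatedness;
2. the percent with at least one such event judged device- or procedure-related.

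State that the split of deaths before 30 days and from 30 days to six months is all-cause. If six-month data have been seen before the change, label these rows as added after data review.

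The cost is a few sentences and some table rows. The CEC already classifies seriousness, device-relatedness and procedure-relatedness, so no new data or follow-up are needed, and without a hypothesis test there is no multiplicity cost. The downside is presentational. Hospitalization alone makes an event serious, and Clinical Need describes these patients as being admitted more and more often, so the first rate will include background heart failure admissions and look less favourable. The second rate is shown with it for that reason.

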defined by the protocol for 30 days or discharge whichever occurs first. Any Sunshine Heart field personnel or designee present for the implant procedure should review the informed consent prior to the procedure to ensure compliance.

In accordance with the ethical principles that have their origin in the Declaration of Helsinki, each patient must be informed about the study and the patient or legal representative must sign and date an agreement acknowledging that participation in the study is voluntary. The Patient Informed Consent Form will be provided to the patient in the language he/she is able to read and understand. (Refer to Appendix H for the sample Consent Form). The original signed Informed Consent will be retained in the individual Participant Study folders, and copies of the signed Informed Consent Form will be provided to the patient and to the hospital medical records of the patient.

Patients shall be consented for follow-up to 10 years.

Patient Withdrawal or Loss to Follow-Up

In the event a patient chooses to withdraw from the clinical study, the investigational site should attempt to ensure that any adverse events are resolved and documented as such. A Study Exit/Death Form must be completed and the patient will no longer be followed in the clinical study.

In the event the patient becomes lost to follow-up, the investigational site should make two documented attempts to contact the patient. A Study Exit/Death Form must be completed and the patient will no longer be followed in the clinical study.

Data Collection Overview

A review of patient files is required to determine preliminary eligibility according to patient inclusion and exclusion criteria. Baseline data including all imaging and functional test must be collected no more than **30** days prior to the implant date.

Follow-up data will be collected at the time of implant, hospital discharge, at planned follow-ups (1-month, 3-month, 6-month, 12-month, 18-month and annually from the implant date thereafter), and “unscheduled” follow-ups (device testing, patient symptoms requiring re-hospitalization, etc.). All adverse events will be collected throughout the study until closure.

Data will be collected via electronic data capture (EDC) screens referred to as e-case report forms (eCRFs). Echocardiogram tapes, and digital storage media must be documented in the patient medical record for source documentation.

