All patient deaths must be documented on the Study Exit/Death Form. If the patient dies during the study, notify the Sunshine Heart field support personnel as soon as possible upon first learning of the death. Follow any IRB requirements for reporting of deaths or adverse events.

In the event of a patient death, efforts should be made to retrieve the implanted device and to obtain an autopsy in order to assess the state of the heart and aorta. A sample of the aorta beneath the C-Pulse® Cuff should be collected for analysis. Please call Sunshine Heart Clinical Support for more instruction. For patients who do not undergo autopsy, written documentation from the investigator will be required regarding circumstances as to why an autopsy was not performed. The device will be analyzed by local staff and Sunshine Heart clinical support personnel according to a standardized device retrieval protocol.

A death summary and an autopsy report are required, please send upon completion to Sunshine Heart to provide to the adjudication committee.

Explant Handling and Final Device Disposition

Promptly call Sunshine Heart Clinical Support for instruction regarding Explant Handling. Cultures should be taken from the device implantation site along with visual analysis and photographs when possible. Explanted products should be returned to Sunshine Heart for analysis.

Complete the Study Exit/Death Form. Report all associated adverse events. Update the Device & Equipment Disposition Log with all products. If the device is not returned to Sunshine Heart, justification must be provided in the log.

Patient Withdrawal and Study Exit

A Study Exit/Death Form shall be completed if patient is unable to or refuses to continue participation in the study. Notify the Sunshine Heart clinical support team as soon as possible upon learning of a patient withdrawal/study exit.

If the patient fails to comply with follow-up visits, the study center must make repeated attempts to contact the patient. Each attempt to contact the patient must be documented in the patient's records and on the Study Exit/Death form.

If the patient officially withdraws from the study, the investigator will document the reason for withdrawal and indicate any relationship of the withdrawal to the study or the device on the Study Exit/Death form.

If a patient withdraws from the study at any time, there will be no penalty or loss of future medical care.

STATISTICAL METHODS AND DATA ANALYSIS

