The secondary objectives are descriptive in nature and will be evaluated in order to gain additional information regarding the C-Pulse® system. There are no specified performance criteria for these objectives. For continuous measures the mean, standard deviation, minimum and maximum values will be presented. For categorical variables the frequency and percent will be presented.

Endpoints consistent with the primary safety and efficacy objectives will be evaluated at all additional time points.

1. The adverse event rate will be presented at 3, 6, 12 and 18 months post-procedure, and annually for years 2-5 post-procedure.
2. The change from baseline to follow-up will be evaluated for peak VO₂, Six Minute Hall Walk, MLWHF, Fatigue Impact Scales and heart failure symptoms from NYHA.

The device failure rate will be quantified. Failure will be defined as both failure of the device, and failure of the device to be programmed to the treatment.

Additionally, the adverse event rate for each of the adverse events described in the Adverse Event Definitions section – pages 36-40 – will be provided. Exact 95% two-sided confidence intervals with an underlying Binomial Distribution will be provided for each event. Adverse events will also be tabulated by attribution (seriousness, device-relatedness, and procedure-relatedness) according to the CEC.

The following additional efficacy measures will be analyzed at each time point to evaluate the efficacy of the C-Pulse® System. For these measures the averages and the average change from baseline to each follow-up period will be presented along with the trend over time:

- Hemodynamic measures are from right heart catheterization (RHC): Cardiac Index (CI), Pulmonary Artery Pressure (PAP), Pulmonary Capillary Wedge Pressure (PCWP), and Cardiac Output (CO).
- Quality of Life
 - Kansas City Questionnaire.
- Blood tests (e.g. Serum sodium, serum creatinine, serum bilirubin, hemoglobin, ALT and AST).
- Concomitant cardiovascular medications

The following measures will also be summarized:

- Re-hospitalization (HF-related and all-cause)
- Duration of support/survival duration.
- Length of time to ICU and hospital discharge
- Device evaluation – Device log and C-Pulse® User log will be evaluated and summarized. Average daily device use will be provided for each time period.

Sample Size Determination

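### Follow-up stops when a patient withdraws or is lost, but the 6-month safety rate is taken over all implanted patients, so event-free leavers count as event-free; support and survival time also has no censoring rule

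*Combined protocol and SAP*

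**What the plan says.** **Stopping follow-up.** Patient Withdrawal or Loss to Follow-Up says, for withdrawal and again for loss: "A Study Exit/Death Form must be completed and the patient will no longer be followed in the clinical study". At withdrawal the site should try to see that adverse events are resolved and documented. For loss, "the investigational site should make two documented attempts to contact the patient". Patient Withdrawal and Study Exit adds: "A Study Exit/Death Form shall be completed if patient is unable to or refuses to continue participation in the study". For missed visits it says that "the study center must make repeated attempts to contact the patient", and it asks for the reason for an official withdrawal and any link to the device.

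**The 6-month rate.** Primary Safety Measures defines the composite as the percentage of patients with at least one listed event "adjudicated by the CEC as device-related out of the total number of patients", through six months. Performance Requirements treats the rate as binomial, reports an exact two-sided 95% interval, and leaves its clinical acceptability to the DSMB. Under Subjects for Analysis, the primary set is every subject in whom the device is placed.

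**Later rates.** Secondary Objectives says that endpoints consistent with the primary ones will be evaluated at the other time points: "The adverse event rate will be presented at 3, 6, 12 and 18 months post-procedure, and annually for years 2-5 post-procedure". Each event type gets an exact binomial interval. No denominator is stated there.

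**Duration.** The same section gives a general rule: "For continuous measures the mean, standard deviation, minimum and maximum values will be presented". Among the measures to be summarised is "Duration of support/survival duration".

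The statistical section contains no censoring rule, number at risk, time-to-event method, missing-data rule or sensitivity analysis for incomplete follow-up.

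**The concern.** A binomial proportion over all implanted patients treats each one as observed for the whole period. Once follow-up stops at exit, that is no longer true. A patient who leaves on day 40 without an event stays in the denominator and can never enter the numerator. A patient with an event before exit is counted correctly, so the error concerns only those who were event-free when they left. It can only lower the rate, and the exact interval does not reflect the missing observation.

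There is no test or threshold, so the observed rate and its interval are the safety evidence on which the DSMB judges success. Sample Size Determination also says that estimates from this study will be used to power the pivotal study. Exit linked to worsening health would make the understatement larger, and nothing in the plan would show by how much.

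Duration of support and survival is a separate matter. For a patient still supported or alive at last contact, the recorded time is a lower bound. A plain mean of such times is too short and depends on when the data are cut.

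**Working it through.** **Inputs.** From the documents: 40 implanted after expansion, a 6-month horizon, a fixed denominator, an exact binomial interval, and later rates to 5 years. Sample Size Determination gives no event rate or exit rate to reproduce, and its extra subjects cover only screen failures. Every event, exit and death rate below is therefore an assumption.

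**1. Six months, expected bias under non-informative loss.** Let the true 6-month risk be p and the 6-month probability of loss be d, with independent constant hazards h = −ln(1−p) and g = −ln(1−d). The expected planned rate is h/(h+g) × [1 − exp(−(h+g))].

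For p = 20%, h = 0.2231:

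| Loss by 6 months | g | Expected reported rate |
|---|---|---|
| 5% | 0.0513 | 19.5% |
| 10% | 0.1054 | 19.0% |
| 15% | 0.1625 | 18.5% |
| 20% | 0.2231 | 18.0% |

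**2. Six months, worst-case bound.** Suppose 40 are implanted, 8 have events and 6 leave event-free.

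- As planned: 8/40 = 20.0% (exact 95% interval 9.1–35.6%).
- Half exposure for leavers (actuarial): 8/(40 − 6/2) = 8/37 = 21.6%.
- Every leaver counted as an event: 14/40 = 35.0% (20.6–51.7%).

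**3. Later years, if the same denominator is used.** Let e, x and m be constant yearly hazards of first device-related event, exit, and death not related to the device.

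- Planned fraction: e/(e+x+m) × [1 − exp(−(e+x+m)t)].
- Fraction with complete follow-up: e/(e+m) × [1 − exp(−(e+m)t)].

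With e = 0.15:

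| t (years) | x | m | Planned | Complete follow-up | Gap (points) |
|---|---|---|---|---|---|
| 2 | 0.15 | 0 | 22.6% | 25.9% | 3.3 |
| 5 | 0.15 | 0 | 38.8% | 52.8% | 14.0 |
| 5 | 0.10 | 0 | 42.8% | 52.8% | 10.0 |
| 5 | 0.15 | 0.10 | 32.4% | 42.8% | 10.4 |

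In the last row, planned is 0.15/0.40 × [1 − exp(−2.0)] = 32.4%, and complete is 0.15/0.25 × [1 − exp(−1.25)] = 42.8%.

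**4. Duration.** Suppose true duration is exponential with mean 5 years and follow-up at data cut is spread evenly over 2 to 5 years. The mean recorded time is the integral of P(duration > t) × P(follow-up > t):

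5(1 − e^−0.4) + (25e^−1 − 10e^−0.4)/3 = 1.648 + 0.831 = 2.48 years.

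The plain mean is about half the true one. This comes from the data cut alone, with no withdrawals assumed.

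**The case against.** **The expected 6-month effect is small.** This stands. A shift of about one point, against an interval of 9.1–35.6%, would not by itself change a clinical judgement. A reader might infer from the bound in step 2 that the plan reports 20% when the truth is 35%. The documents do not support that: it would need 15% of implanted patients (6/40) to leave event-free and every one of them then to have a device-related event.

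**Later denominators and the mean for duration are not stated.** This also stands. Only the 6-month composite names a denominator; the yearly rule is inferred from the wording about consistent endpoints. The line on duration says only that it will be summarised, so mean and SD follow from the general rule. Even the 6-month set is blurred: Justification of Methodology speaks of patients who maintain counterpulsation for six months or longer, and the secondary set is limited to followed-up subjects. The explicit definitions still put all implanted patients in the primary rate.

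**Some informative exits are already captured.** This is true in part. A device problem adjudicated as a device-related adverse event counts before exit, and reasons for withdrawal are recorded. System Modifications keeps the visit schedule after component removal. None of this captures an event that occurs after exit.

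**Constant hazards may overstate the later gap.** This is fair. The protocol describes device risks as front-loaded and reports early infection in the pilot; early events make later exits matter less.

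**Three further inferences do not hold.** A reader might conclude that every error here flatters the device, but understated duration makes it look worse. The two contact rules might look contradictory, but two documented attempts and repeated attempts are compatible. Exit for being unable to continue might be taken to mean too ill to attend, but the text does not say so.

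**The study is descriptive and unpowered.** That limits the seriousness, since no test or error rate is affected. It also means that the estimate and its interval carry all the weight.

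**Conclusion.** The point holds. As written, the plan ends follow-up at withdrawal or loss and divides by all implanted patients, so event-free leavers are counted as event-free and the 6-month device-related rate can only be lowered by this. The expected bias at 6 months is small if loss is non-informative: 1.0 point at 10% loss and 1.5 points at 15%, for a true 20%. The bound under the worst case is 35.0% against 20.0%. The main gap at 6 months is that the plan gives no count of incomplete follow-up and no bound, so the DSMB could not tell which situation it was in.

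If the same denominator is used later, the understatement at 5 years is material: 10 to 14 points in the scenarios shown, under assumed constant hazards and non-informative exit. Competing death reduces it but does not remove it.

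The treatment of support and survival time is a second, separate weakness. It arises mainly from patients still supported or alive at the data cut, and it understates duration.

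The plan should be changed, but the study is not invalidated.

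**What to change.** 1. **Patient Withdrawal or Loss to Follow-Up, and Patient Withdrawal and Study Exit.** Separate stopping visits from stopping data. Unless consent for it is withdrawn, keep collecting vital status, device status and serious adverse events by phone or record review to 6 months, then yearly. Check whether the consent form already allows this; it was not available for review.
2. **Primary Safety Measures, Performance Requirements and Secondary Objectives.** Keep the binomial rate and state its denominator at every time point. Beside it, report cumulative incidence censored at last contact, with death not related to the device as a competing event. Give the number with incomplete follow-up, and a bound that counts those patients as events.
3. **Secondary Objectives, duration.** Report survival by Kaplan-Meier, and duration of support by cumulative incidence of its ways of ending (death, LVAD or transplant, device stopped), instead of mean and SD.

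The cost is some wording, a few extra contacts per exited patient, possibly a consent line, and a somewhat less favourable reported safety rate. Outcomes not recorded after exit may not be recoverable later, so the first change is the most urgent.
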